3.2 NRS30

With historical placebo rate at 26%, the following scenarios of the proportion of subjects achieving NRS30 at Week 12 were evaluated to assess the power and false positive rates with different number of matched subjects:

Scenario	Placebo Rate	Upadacitinib Rate*
In-trial PBO rate = Historical rate – 10%	0.16	0.46
In-trial PBO rate = Historical rate – 5%	0.21	0.46
In-trial PBO rate = Historical rate	0.26	0.46
In-trial PBO rate = Historical rate + 5%	0.31	0.46
In-trial PBO rate = Historical rate + 10%	0.36	0.46

* Assume that upadacitinib performs at least as good as min TPP.

One-sided power and false positive rates for each scenario and different numbers of matching subjects were calculated, and the results from 10000 simulations (random seed: 12345) are summarized in the following table:

	Power				False Positive Rate			
	Number of Matched Subjects			In-Trial Only	Number of Matched Subjects			In-Trial Only
Scenario	23	46	68	UPA vs PBO: 45:23	23	46	68	UPA vs PBO: 45:23
Historical rate - 10%	0.813	0.788	0.775	0.899	0.006	0.001	0	0.094
Historical rate - 5%	0.721	0.723	0.724	0.769	0.014	0.006	0.003	0.084
Historical rate (Base case)	0.625	0.65	0.668	0.603	0.03	0.018	0.012	0.077
Historical rate + 5%	0.521	0.573	0.607	0.434	0.057	0.045	0.038	0.077
Historical rate + 10%	0.41	0.492	0.542	0.279	0.089	0.098	0.096	0.073
Historical rate + 11%*	0.391	0.476	0.528	0.249	0.099	0.112	0.115	0.073

* To determine the cutoff number in the matched subjects, additional scenario of historical rate + 11% is also conducted and the power and false positive rate are given in the above table.

The same conclusion can be reached with the results provided from the simulations.

The numbers of matched placebo subjects are given in the following table using the same criteria as for HiSCR:

In-Trial PBO Rate	Number of Matched Subjects
≤ 36%	68
>36% and ≤ 37%	23
>37%	0

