3.2 Secondary Endpoint(s)

The secondary endpoint is the achievement of NRS30, defined as at least 30% reduction and at least 1 unit reduction from Baseline in Patient's Global Assessment (PGA) of Skin Pain (numeric rating scale [NRS]) – at worst at Week 12 among subjects with baseline $NRS \geq 3$.

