2.1 Simulation of Baseline Covariates and Treatment Groups

Within each simulation, the following baseline covariates were generated for the 68 in-trial subjects from multivariate normal distribution:

- Age
- Baseline AN count
- Baseline BMI
- Duration of HS since diagnosis
- Baseline draining fistula
- Gender
- Race
- Smoking status

The multivariate normal distribution with mean vector μ , standard deviation S and correlation matrix Σ is defined as below (covariates in the order as listed above):

$$\mu' = (35.8, 21.8, 35.2, 11, 3.56, 0, 0, 0)$$

$$S' = (11.91, 20.73, 8.65, 8.4, 5.14, 1, 1, 1)$$

$$\Sigma = \begin{pmatrix} 1 & 0 & 0 & 0.4 & 0.1 & 0 & 0 & 0 \\ 0 & 1 & 0.1 & 0 & 0.3 & 0 & 0 & 0 \\ 0 & 0.1 & 1 & 0 & 0 & 0 & 0 & 0 \\ 0.4 & 0 & 0 & 1 & 0 & 0 & 0 & 0 \\ 0.1 & 0.3 & 0 & 0 & 1 & 0 & 0 & 0 \\ 0 & 0 & 0 & 0 & 0 & 1 & 0 & 0.1 \\ 0 & 0 & 0 & 0 & 0 & 0 & 1 & 0.2 \\ 0 & 0 & 0 & 0 & 0 & 0.1 & 0.2 & 1 \end{pmatrix}$$

The means and standard deviations for the continuous variables were estimated based on the baseline information from the in-trial subjects. For the binary variables, random

samples were generated using standard normal distribution and the binary outcome of 0 or 1 was determined by the proportions estimated from the in-trial subjects.

Based on the baseline information from 68 in-trial subjects, the two stratification factors, baseline Hurley Stage (<III, III), and the indicator of prior exposure to anti-TNF treatment (Yes, No) were generated assuming that 5% of the subjects are Hurley Stage <III and have prior exposure to anti-TNF treatment, 10% of the subjects are Hurley Stage III and have prior exposure to anti-TNF treatment, 55% of the subjects are Hurley Stage <III and do not have prior exposure to anti-TNF treatment, and 35% of the subjects are Hurley Stage III and do not have prior exposure to anti-TNF treatment.

Treatment groups (upadacitinib 30 mg and placebo) were generated in a 2:1 ratio within each of the 4 strata. With a total of 68 subjects, it was assumed that 45 subjects received upadacitinib 30 mg, and 23 subjects received placebo.

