2.2 Matching Historical Placebo Subjects Using Propensity Score

In the matching phase, placebo subjects from existing studies (Study M11-313, Study M11-810, Study M16-833) were matched in a fixed ratio with in-trial subjects using propensity score method with pre-selected baseline covariates. Nearest neighbor matching method was used.

Different numbers of matched subjects were evaluated:

Number of Matched Subjects	Matching Ratio (in-trial: matching)	Control Set
23	1:1	In-trial placebo subjects (N=23)
46	1:2	In-trial placebo subjects (N=23)
68	1:1	All in-trial subjects (N=68)

3.0 Scenarios and Simulation Results for Primary Endpoint (HiSCR) and Secondary Endpoint (NRS30)

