The simulation results show that power with matched placebo subjects from historical data is higher than that with in-trial placebo subjects only in all of the scenarios. Power increases with the increase in the number of matched placebo subjects. In the meantime, when the in-trial placebo rate is lower than or similar to the historical placebo rate, the false positive rates are controlled at approximately 0.05. When the in-trial placebo rate is higher than historical placebo rate, the false positive rate increases with the increase in the number of matched subjects. The inflation in the false positive rate is larger when higher in-trial placebo rate is observed. The number of matched subjects is therefore determined by both achieving a high power and maintaining a slightly inflated false positive rate.

To determine the number of matched placebo subjects in the analysis, the following two criteria should be satisfied:

- One sided false positive rate is controlled at 10%;
- Not to exceed 68 (approximately 3 times the number of in-trial placebo subjects).

The numbers of matched placebo subjects are given in the following table:

In-Trial PBO Rate	Number of Matched Subjects
≤ 33%	68
>33% and ≤ 34%	23
>34%	0

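### The NRS30 simulation table behind the 36%/37% borrowing cut-offs does not reproduce from its stated inputs, so the 10% false-positive limit is not shown

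*SAP*

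**What the plan says.** SAP 9.4.1 plans a supplemental NRS30 comparison of upadacitinib with in-trial placebo plus 68, 23 or 0 historical placebo subjects. The number depends on the in-trial placebo rate, with cut-offs at 36% and 37%. These come from Appendix F 3.2: "With historical placebo rate at 26%, the following scenarios of the proportion of subjects achieving NRS30 at Week 12 were evaluated". The upadacitinib rate is 46% in every scenario. For arm sizes, Appendix F 2.1 says "it was assumed that 45 subjects received upadacitinib 30 mg, and 23 subjects received placebo".

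The criterion, set in Appendix F 3.1 and reused for NRS30, is "One sided false positive rate is controlled at 10" per cent, with at most 68 matched subjects. On the source of the controls, Appendix F 2.2 says "placebo subjects from existing studies (Study M11-313, Study M11-810, Study M16-833) were matched in a fixed ratio with in-trial subjects". It does not say whether their outcomes were held fixed or drawn at random, or at what rate.

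For HiSCR, Appendix F 3.1 concludes that "power with matched placebo subjects from historical data is higher than that with in-trial placebo subjects only in all of the scenarios". For NRS30, Appendix F 3.2 says "The same conclusion can be reached with the results provided from the simulations".

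**The concern.** Two features of the printed tables prompt the check.

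- **Error rates.** With 68 matched subjects and an in-trial rate 10 points above the historical rate, the HiSCR table gives a false-positive rate of 0.189 (28% against 38%). The NRS30 table gives 0.096 (26% against 36%). Sample sizes and gap are the same and the rates differ by 2 points, so binomial variance cannot halve the error.
- **Power.** At 10 points below the historical rate, NRS30 power is 0.899 in-trial only and 0.813, 0.788 and 0.775 with 23, 46 and 68 matched. At 5 points below, it is 0.769 against 0.721-0.724. That is the reverse of the HiSCR conclusion the text carries over.

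At stake is the borrowing rule. If the matched subjects respond at 26%, the plan would add 68 of them at in-trial rates where the error is up to about twice its own limit.

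**Working it through.** **Inputs.** One-sided alpha 0.05 (SAP 9.1). Arms 45:23 and four strata by prior anti-TNF and Hurley stage (Appendix F 2.1), with shares rescaled to 100%. HiSCR: historical 28%, upadacitinib 59% (Appendix F 3.1). NRS30: historical 26%, upadacitinib 46% (Appendix F 3.2). For the false-positive rate, upadacitinib is assumed to respond at the in-trial placebo rate.

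**Hand check, ignoring strata.** Let p be the in-trial rate, h the matched rate and m = 68, with outcomes held fixed.

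- Pooled control rate c = (23p + 68h)/91, and bias d = p − c.
- Estimated SE = √[p(1−p)/45 + c(1−c)/91].
- True SE = √[p(1−p)/45 + 23p(1−p)/91²].
- False-positive rate = P(Z > (1.645·estimated SE − d)/true SE).

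*HiSCR first*, p = 0.38, h = 19/68: c = (8.74 + 19)/91 = 0.305, d = 0.075, SEs 0.0870 and 0.0767. Then (0.1431 − 0.0752)/0.0767 = 0.885, giving **0.188** (SAP 0.189).

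*NRS30*, p = 0.36, h = 18/68: c = (8.28 + 18)/91 = 0.289, d = 0.071, SEs 0.0859 and 0.0759. Then (0.1413 − 0.0712)/0.0759 = 0.923, giving **0.178** (SAP 0.096).

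In-trial-only power is Φ(Δ/SE − 1.645), with SE = √[a(1−a)/45 + b(1−b)/23] for response rates a (upadacitinib) and b (placebo), and Δ = a − b:

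- HiSCR base case: 0.31/0.1189 = 2.607, power **0.832** (SAP 0.837).
- NRS30 base case: 0.20/0.1178 = 1.697, power **0.521** (SAP 0.603).

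**Stratified simulation.** 10,000-40,000 trials per cell. Stratum weight w = n₁n₀/(n₁+n₀); MH risk difference = Σw(p₁−p₀)/Σw. Three statistics were used: MH difference with Wald variance, MH difference with Sato variance, and CMH. Historical outcomes were either fixed (6/23, 12/46, 18/68) or Bernoulli at 26%.

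HiSCR, 68 matched, fixed outcomes, Wald: false-positive rates 0.001/0.007/0.028/0.087/0.105/0.197 against SAP 0.002/0.009/0.033/0.091/0.108/0.189. In-trial-only power agrees within 1.3 points in all six scenarios.

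NRS30, 68 matched, false-positive rate:

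| In-trial rate | SAP | Range over variants |
|---|---|---|
| 26% | 0.012 | 0.02-0.05 |
| 31% | 0.038 | 0.07-0.12 |
| 36% | 0.096 | 0.17-0.23 (fixed 0.172-0.186; random 0.217-0.232) |
| 37% | 0.115 | 0.20-0.26 |

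A continuity correction lowers the 36% figure only to 0.15-0.18. The 10% limit is crossed between 29% and 30% with random outcomes (0.080-0.088, then 0.095-0.104) and between 32% and 33% with fixed outcomes (0.088-0.095, then 0.105-0.111). With 23 matched at 37%, the rate is 0.10-0.16 (SAP 0.099), or 0.06-0.09 with continuity correction, so that tier is borderline.

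NRS30 in-trial-only power, Wald (the closest statistic):

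| Placebo rate | 16% | 21% | 26% | 31% | 36% | 37% |
|---|---|---|---|---|---|---|
| SAP | 0.899 | 0.769 | 0.603 | 0.434 | 0.279 | 0.249 |
| Recomputed | 0.881 | 0.738 | 0.566 | 0.392 | 0.245 | 0.218 |

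All six are 2-4 points below the SAP, and Monte Carlo error at 10,000 runs is at most 0.5 point. An upadacitinib rate of 47-48% would reproduce this row. It would also move base-case power with 68 matched, already 0.75-0.77, further from the stated 0.668.

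**Side checks.**

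- Appendix F 2.1 gives strata of 5%, 10% and 55%, and then "35% of the subjects are Hurley Stage III and do not have prior exposure to anti-TNF treatment". The sum is 5 + 10 + 55 + 35 = 105%. Four versions totalling 100% change the error at 36% by under 1 point.
- SAP 3.2 defines NRS30 "at worst at Week 12 among subjects with baseline" NRS of at least 3, yet the simulation uses all 68 in-trial subjects. With assumed subsets of 40:20 to 32:16, the error at 36% stays 0.16-0.23 and base-case in-trial-only power falls to 0.38-0.53.

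**The case against.** The best reply is that 26% anchors the scenarios and need not be the response rate of the matched subset, since matching real subjects can select a group that differs from its pool. The outcome model is also unstated, and strongly prognostic strata would raise in-trial-only power. Combining the two gives a table close to the SAP's. With assumed matched outcomes of 7/23, 14/46 and 21/68 (about 30-31%) and an assumed Hurley III log-odds of −1.5, 40 of 48 cells fall within 2 points and the largest gap is 3.6. The error with 68 matched at 36% is then 0.095, and the reversed power pattern appears.

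This stands as a possible explanation, and it is why the cut-offs cannot be called wrong outright. It does not rescue the table as documented. It needs two inputs that the SAP does not state, and in-trial-only power is still low in all six scenarios (0.894/0.763/0.591/0.419/0.255/0.225). The subject list in Appendix G is not in the text available for review and is not counted as an omission.

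The stakes are also limited. This is a proof-of-concept study without multiplicity control, and an in-trial-only comparison is planned as well.

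**Conclusion.** The concern holds. The inputs stated in Appendix F 3.2 do not produce its table under any test or outcome variant tried, while the same code closely reproduces HiSCR. The worst false-positive gap over 18 cells is 9-14 points for NRS30 and 2-4 points for HiSCR. An unusual matched set alone cannot explain this, because the in-trial-only power column also fails. The sentence equating the NRS30 and HiSCR conclusions is contradicted by the table itself, without any simulation.

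Confidence is high that the table does not reproduce. That the 10% limit is breached is conditional: if the matched subjects respond at 26%, 68 controls meet it only up to about 29-32%. The documents do not show which input is wrong. The effect is confined to a supplemental analysis of the secondary endpoint. The primary HiSCR test and the one-sample NRS30 test against 22.5% are untouched. This should be corrected, but it does not threaten the main result.

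**What to change.** Before database lock:

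1. State the NRS30 response rate of the matched subjects, the upadacitinib rate actually simulated, and how historical responses were generated (fixed or random, and any dependence on strata).
2. Rerun with the number of in-trial subjects whose baseline NRS is at least 3, and with stratum shares totalling 100%.
3. Replace the Appendix F 3.2 table, and reset the cut-offs there and in SAP 9.4.1 to values that meet the 10% criterion. If 26% is confirmed, the 68-subject cut-off falls to around 29-32%, depending on how outcomes were generated.
4. Replace the sentence that carries over the HiSCR conclusion with one that describes the NRS30 power columns.
5. Explain any gap between the matched-set rate and the 22.5% null. Neither need be wrong: the null comes from two studies and the matched set from three.

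The cost is one simulation rerun and a SAP table update, with fewer borrowed controls if the cut-off drops. A correction made after unblinding would look data-driven.

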7.1 Demographics and Baseline Characteristics

Demographics and baseline disease characteristics will be summarized for ITT Population.

Continuous demographic variables include age, weight, height, and body mass index (BMI). Categorical demographic variables include sex, ethnicity, race, age (<40 , $40 - 65$, ≥ 65 years), weight (≤ 100 or > 100 kg), BMI (< 25 , $\geq 25 - < 30$ or ≥ 30 kg/m²), tobacco user (current, former, never, unknown), and alcohol user (current, former, never, unknown).

Disease characteristics include HS disease duration in years, Baseline lesion counts (by lesion type), Baseline skin pain NRS (among all subjects and among subjects with baseline value ≥ 3), Baseline DLQI, Baseline HSSA, Baseline HSIA and Baseline hsCRP as continuous variables, prior exposure to TNF antagonists (yes, no) and baseline Hurley stage ($< III$, III), HS history (anatomic regions, types of lesions) as categorical variables.

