9.4 Secondary Efficacy Analyses

9.4.1 Main Analyses of Secondary Efficacy Endpoints

The secondary endpoint NRS30, defined as the achievement of at least 30% reduction and at least 1 unit reduction from Baseline in Patient's Global Assessment (PGA) of Skin Pain (numeric rating scale [NRS]) – at worst at Week 12 among subjects with baseline NRS ≥ 3 .

NRS30 will be analyzed using the same method as for the primary endpoint and comparing with the historical placebo rate (22.5%) at Week 12. The historical placebo rate of 22.5% is assumed based on the response rate of placebo subjects from the two Humira studies (Study M11-313 and Study M11-810), who satisfied the same eligibility criteria.

The same supplemental analysis to compare upadacitinib 30 mg group vs in-trial placebo group combined with pre-selected placebo subjects' data from the three existing trials will also be performed as described in Section 9.3.3. The actual number of synthetic placebo subjects is determined as below (simulation details can be found in [Appendix F](#) and the list of matching subjects can be found in [Appendix G](#)):

In-Trial Placebo Rate	Number of Synthetic Placebo Subjects
$\leq 36\%$	68
$>36\%$ and $\leq 37\%$	23*
>37	0

* The 23 subjects with the highest rank in [Appendix G](#) Table B will be used in the analysis.

Comparison between the in-trial data of the upadacitinib group and the in-trial placebo subjects will also be performed. The analysis method will be the same as described in Section 9.3.3.

In addition, analgesic use will be handled as follows:

- Prohibited analgesic (including opioids): A subject will be counted as a non-responder from the day that the subject initiates prohibited analgesic to 5 days after the end of such analgesic use.
- Protocol-allowed analgesic use:
 - A subject who enter the study without concomitant analgesic will be counted as a non-responder from the day that the subject initiates a protocol-allowed analgesic to 2 days after the end of such analgesic use.
 - A subject who entered the study on a stable dose of a protocol-allowed concomitant analgesic will be counted as a non-responder from the first day of an analgesic dose increase to 2 days after the end of the dose increase.

The NRI-C will be the primary approach for missing data handling in the analysis of the secondary efficacy endpoint. NRI-NC will be used as sensitivity analysis.

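### Appendix F 3.2 simulates the supplemental NRS30 comparisons on all 45:23 randomised subjects, although NRS30 is analysed only in those with baseline NRS ≥ 3; the stated power is too high if any subject falls below 3

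*SAP*

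**What the plan says.** SAP 9.4.1 defines NRS30 as a pain response "at worst at Week 12 among subjects with baseline NRS ≥ 3". SAP 3.2 and Protocol 3.2 carry the same restriction. The eligibility criteria in Protocol 5.1 set no minimum pain score. SAP 7.1 treats the restricted group as distinct from the whole, planning a summary of "Baseline skin pain NRS (among all subjects and among subjects with baseline value" 3 or above.

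Appendix F 2.1 builds the simulated trial from 68 in-trial subjects: "it was assumed that 45 subjects received upadacitinib 30 mg, and 23 subjects received placebo". Its covariate list has no baseline pain score. Appendix F 3.2 introduces the NRS30 runs with "With historical placebo rate at 26%, the following scenarios of the proportion of subjects achieving NRS30 at Week 12 were evaluated", and its results table keeps the column label "UPA vs PBO: 45:23", the same as for HiSCR.

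The borrowing sizes come from the full sample too. In Appendix F 2.2, 68 is a 1:1 match to all 68 in-trial subjects and 23 is a 1:1 match to the 23 placebo subjects. The limit is written in Appendix F 3.1 as "Not to exceed 68 (approximately 3 times the number of in-trial placebo subjects"). Appendix F 3.2 and SAP 9.4.1 apply the same criteria to NRS30: 68, 23 or 0 borrowed subjects, according to the in-trial placebo rate.

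**The concern.** The simulation and the analysis it supports appear to use different sets of subjects. Nothing in Appendix F reduces the sample for NRS30, so unless every randomised subject has a baseline score of at least 3, the power in 3.2 describes a larger trial than the one analysed.

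Two things depend on it. One is the stated power of the supplemental NRS30 comparisons, in-trial only and with borrowed placebo. The other is the weight of the historical data: 68 was presented as about three times the in-trial placebo group, and against a smaller qualifying group the same 68 would dominate the control arm more than that explanation suggests.

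**Working it through.** **Inputs.** From Appendix F 3.2: placebo 26%, upadacitinib 46%, 45:23. From SAP 9.1: one-sided 0.05. From SAP 9.3.3 and the sample code in Appendix E: a stratified comparison using the Mantel-Haenszel risk difference. From Appendix F 2.1: strata of 5, 10, 55 and 35%, which sum to 105% and were rescaled to 100%. The share with baseline NRS ≥ 3 is not given and is assumed to be 60 to 90%.

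**Test simulated.** d = Σ w_s(p1_s − p0_s) / Σ w_s, with w_s = n1_s·n0_s/(n1_s + n0_s), Greenland-Robins variance and 2:1 allocation within strata; reject if d/SE > 1.645.

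**Reproducing the SAP at 45:23, in-trial only.** The order is −10, −5, 0, +5, then the extra scenario (+6) and +10 for HiSCR, and +10 then +11 for NRS30.

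| Quantity | Computed | SAP |
|---|---|---|
| HiSCR power | 0.976, 0.927, 0.837, 0.705, 0.679, 0.554 | 0.977, 0.926, 0.837, 0.701, 0.672, 0.549 |
| NRS30 false-positive rate | 0.088, 0.084, 0.077, 0.076, 0.073, 0.073 | 0.094, 0.084, 0.077, 0.077, 0.073, 0.073 |
| NRS30 power, base case | 0.56 | 0.603 |

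The method matches the first two rows closely but not the third. At 46% versus 26%, a trial of 51:26 gives 0.597, so a smaller subset cannot explain 0.603. An upadacitinib rate of 0.47 gives 0.593 and 0.48 gives 0.619. This gap is separate from the subset question, so the subset effect below is measured from the computed full-size value and not from 0.603.

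**Effect of the restriction, 46% versus 26%.** The last column assumes a matched rate of 31%.

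| Assumed share | Sizes | In-trial-only power | Fall (points) | Power with 68 borrowed |
|---|---|---|---|---|
| 100% | 45:23 | 0.56 | – | 0.59 |
| 90% | 40:21 | 0.54 | 2 | 0.56 |
| 80% | 36:18 | 0.51 | 5 | 0.52 |
| 60% | 27:14 | 0.45 | 11 | 0.45 |

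Repeat simulations start from 0.54 to 0.56 at full size and give falls of 2-3, 5-6 and 11-12 points. With 68 borrowed the falls in the table are 3, 7 and 14 points.

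The 31% is a fitted value, not the SAP's. With a matched rate near 26%, the false-positive rate at a 36% placebo rate with 68 borrowed would be about 0.22, against the 0.096 printed. A second fit (matched 32%, upadacitinib 48%) gives 0.646 at full size against the stated 0.668, then 0.611, 0.579 and 0.499 at the three shares. That is a fall of 3.5, 6.7 and 14.7 points.

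**Borrowing ratio, if all 68 borrowed subjects have NRS ≥ 3.** 68/23 = 2.96; 68/21 = 3.24; 68/18 = 3.78; 68/14 = 4.86. Three times the qualifying placebo count would be 63, 54 and 42. The ratio passes 3.0 once 22 or fewer placebo subjects qualify (68/22 = 3.09).

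**False-positive rate at the cut-offs (matched rate 32%).** With 68 borrowed at a 36% placebo rate: 0.102 at full size and 0.101 to 0.105 for shares of 50 to 95%. With 23 borrowed at 37%: 0.092 at full size, 0.097 at 80%, 0.099 at 60%.

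**Main NRS30 test.** One-sample against 22.5%, normal approximation: power = Φ[(0.46 − 0.225 − 1.645·√(0.225·0.775/n)) / √(0.46·0.54/n)]. This gives 0.96 at n = 45, 0.93 at 36 and 0.86 at 27.

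**The case against.** The strongest reply is that little depends on this simulation. The main NRS30 analysis is the one-sample test against 22.5%, the sample-size section claims no power for NRS30, and Appendix F exists to choose how many historical subjects to borrow. That choice is driven by the 10% false-positive criterion, which hardly moves. All of this stands, and it limits the point to the supplemental comparisons.

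A reader might infer that the SAP's borrowing cap is broken. The documents do not support that. The written limit is the number 68, and borrowing 68 does not exceed it; the factor of three is an explanation beside the number. At shares of 90 to 95% the ratio is 3.1 to 3.2, which still fits that explanation. The higher ratios also require that all 68 borrowed subjects have NRS ≥ 3. NRS30 has its own ranked list (Appendix G Table B), which is not in the reviewed text. If the restriction removed the same share from both groups, the ratio would stay near 3.

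A reader might also attribute the whole distance from 0.603 or 0.668 to the restriction. About 4 to 6 points in-trial, and a similar amount in the borrowed runs under the 31% fit, are already there at the full 45:23 and have another cause.

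Finally, it could be inferred that the 36% and 37% cut-offs are wrong. No calculation shows that.

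What survives is the mismatch itself: the table is labelled and sized for all randomised subjects, and the endpoint is not.

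**Conclusion.** The point holds, conditionally and for the supplemental NRS30 analyses only. If any randomised subject has baseline NRS below 3, Appendix F 3.2 states power for a larger sample than will be analysed. The loss is small at a 90% share (about 2-3 points in-trial only), moderate at 80% (5-6) and material at 60% (10-12), and similar or somewhat larger with 68 borrowed. These sizes rest on an assumed share. The borrowed-placebo figures rest also on a matched rate fitted to the SAP's false-positive column, since the stated 26% does not reproduce it. The factor-of-three explanation for 68 weakens at the lower shares, provided the borrowed subjects all qualify. The cut-offs are not shown to be wrong, though the SAP's own values beside them (0.096 and 0.099) leave little room under 10%, so they deserve confirmation. The main one-sample NRS30 test is not affected by this simulation.

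**What to change.** Before database lock, re-run Appendix F 3.2 with the actual number of randomised subjects per arm with baseline NRS ≥ 3, and restrict the borrowed subjects in the same way. Baseline data from the in-trial subjects already set the simulation inputs, so the counts should be obtainable without outcome data. Then:

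- restate the NRS30 power, in-trial only and with borrowing;
- write the NRS30 borrowing cap as three times the in-trial placebo count with NRS ≥ 3;
- confirm that the 36% and 37% cut-offs still meet the 10% criterion;
- state in SAP 9.4.1 that the borrowed subjects are also limited to NRS ≥ 3.

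The cost is one re-run of an existing simulation and a lower stated power for a supplemental analysis.
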